Intensive home blood pressure lowering in advanced chronic kidney disease: a pilot randomized controlled trial

Study Protocol

NCT02975505

Document date: February 13, 2025

Study design

This pilot study is a non-blinded randomized controlled trial investigating the safety and feasibility of strict blood pressure control in patients with advanced CKD. Patients will be randomized in 2:1 ratio to intervention (home SBP target < 120 mmHg) or usual care (home SBP target 130-140 mmHg) until 75 patients are enrolled, and then subsequently patients will be randomized in 1:1 ratio to intervention or usual care. Antihypertensive medications will be titrated as needed to achieve target home SBPs over the course of 4 months and maintained thereafter until study closeout (see Figure 1). Biannual visits are conducted after month 12.

Study population

All patients are recruited from the University of California San Francisco nephrology clinics. Inclusion and exclusion criteria are as follows:

Inclusion criteria:

- 1. ≥ 18 years of age
- 2. English-speaking
- 3. Patients with advanced CKD who meet the eGFR criteria defined as either
 - a. at least two eGFRs ≤30 mL/min/1.73m² in the last three months
 - b. a prior diagnosis of CKD and at least one eGFR ≤30 mL/min/1.73m² in the last three months.
- 4. Presence of elevated BP, defined as receipt of one or more antihypertensive agents or an office SBP>140 mmHg at the time of the screening visit. If the participant is not on antihypertensive medications, they must have an average home SBP>130 mmHg during the first week of the study when baseline home BPs are ascertained.
- Participants must have a mid-arm circumference between 22-37 cm and access to a smart phone or tablet in order to use the Bluetooth-enabled home BP device, QardioArm[®].

Exclusion criteria:

Patients are excluded if they:

- 1. are planning to become pregnant or are currently pregnant
- 2. are marginally housed due to concerns regarding follow-up
- 3. are institutionalized or a prisoner
- 4. are actively participating in a different interventional trial that may affect blood pressure
- 5. are actively abusing illicit drugs and alcohol
- 6. have a history of poor compliance
- 7. take >5 antihypertensive medications (including diuretics) at maximum doses
- have cognitive impairment and are unable to follow instructions regarding home BP measurement during screening visit

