Once patients are screened and deemed eligible, study personnel will notify nephrologists of their patients' eligibility and obtain assent for patient participation in the trial prior to randomization. Stratified permuted-block randomization will be performed with stratification by diabetes status in order to ensure that patients with diabetes who have previously been excluded from many trials of intensive BP lowering (8–10) are represented in our pilot study. Investigators will be blinded to the ordering of the randomization blocks and their respective sizes. The generation of allocation sequence is performed by and only accessible to the study coordinator for assignment of participants to the intervention and not accessible to investigators. Patients are contacted via phone or secure messaging to begin active titration of their antihypertensive regimens to achieve their assigned target SBPs after randomization.

Home blood pressure monitor

QardioArm[®] is a wireless Bluetooth-enabled home BP monitor that is validated by the European Society of Hypertension Protocol and the American Heart Association (31) and has a strong direct linear correlation (r=.96) with the previously validated and widely accepted Omron M3[®] BP device (32). The device is compatible with most smartphones and allows for real-time

wireless transmission of BP readings through an online phone application. The device is also accompanied by a secure platform used by providers for BP data transmission, monitoring, download, and storage. All participants are provided a device at no cost, and Bluetooth linkage between the device and smartphone are setup by study personnel at the baseline visit.

Office BP readings during study visits

Office BPs are measured at the baseline, 2, 4, 8, and 12-month study visits (Figure 1), and every six months thereafter. Participants are seated quietly in a room with the study coordinator for 5 minutes before BPs are taken. Three measurements are taken one minute apart. Participants are then be asked to stand for two minutes and two standing BPs are recorded one minute apart. One study coordinator will be present during all office BP measurements.

Intervention

Blood Pressure Targets

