We have chosen to target home SBP, as opposed to mean arterial pressure (MAP) or diastolic BP (DBP) based primarily on the CV and mortality benefits seen recently in SPRINT (8) and data that suggest that SBP is a stronger predictor of ESKD risk and CV disease than DBP or MAP (24,33,34). Our usual care group will be treated to home SBP targets of 130-140 mmHg (equivalent to office SBP of 135-145 mmHg) because this was the range of BPs that screened patients had at baseline enrollment under routine care. During routine clinical care, any non-study provider can titrate antihypertensive agents as per their preference outside of the study protocol based on the clinic BP readings and other data available to them, and such titrations are noted and will be accepted by the study team. Home BP readings are made readily available to non-study providers upon request, and all nephrology clinic providers are alerted of patient enrollment in the study and the assigned BP target following randomization.

Home blood pressure readings

Participants are asked to measure their BPs at home on any three days of the week. For each day, participants take 3 readings in the morning and 3 in the evening. Participants are instructed to rest for 5 minutes before taking readings and sit quietly for 1 minute in between readings. Weekly home BP averages are calculated from the most recent 18 readings in a given week. Antihypertensive medications will be titrated by study investigators based on the average of the most recent 18 home BP measurements received, with a minimum of 6 required readings per week to be considered sufficient for any changes to medications. An insufficient number of measurements will prompt contact with the participant to increase the number of readings.

Antihypertensive Therapy Titration Intervention

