We will permit up to a 30% increase in serum creatinine level after ACEi/ARB initiation or uptitration of dosages of other antihypertensive medications, in accordance with traditional guidelines and published literature (35,36). For patients who experience >30% increase in serum creatinine, the ACEi/ARB dose or other antihypertensive medication will be reduced, with plans for a repeat serum creatinine within 2 weeks. If the serum creatinine continues to be elevated, then the ACEi/ARB will be discontinued. We will also respect the opinion of the patient's nephrologist on this issue. If a nephrologist is concerned about any rise in serum creatinine, we will reduce or discontinue the drug. We will then proceed with the next suggested class of antihypertensive agents to help achieve the target blood pressure.

During the first 8 months of the study, participants will be contacted every other week by study coordinators to note any adverse events including dizziness, falls, syncope, hospitalizations, emergency room visits, acute kidney injury, CV events, or allergic reactions, as well as adherence to medication regimen and medication side effects such as diuresis, impotence, cough, lack of energy and sleepiness, lightheadedness on standing, or headaches.

Laboratory Tests

Basic metabolic panel and urine chemistry laboratory tests are obtained at baseline and at months 1, 2, 4, 8, 12, and every six months thereafter but timed as closely to clinical laboratory tests as possible (to avoid additional burden on participants) in a pragmatic approach. Labs are closely monitored by study investigators and medications titrated

accordingly to ensure the safety of all participants. Additional laboratory testing is performed as needed.

Follow-Up Timeline

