Safety of our intervention will also be a secondary outcome and will be determined by a composite of adverse events including hyperkalemia ($K \ge 6.0 \text{ meq/L}$), self-reported falls, syncope, or acute kidney injury (AKI) requiring emergency room visit or hospitalizations. Discharge summaries from emergency room visits and hospitalizations in patient health records will be reviewed and events adjudicated by two study investigators. In addition, onset of ESKD will not be a censoring event; patients will be encouraged to continue to check home BPs following transplant or dialysis, but no study-driven active titration of antihypertensive agents will occur after ESKD onset.

Statistical analysis

Safety outcomes, or rates of adverse events, will be tallied using simple proportions and descriptive statistics. Intention-to-treat analysis will be performed. Stratified analyses by diabetes status will be performed given the lack of robust trial data to support intensive BP lowering in patients with diabetes. We will also test for differences in the composite rates of hospitalizations, emergency room visits, and hyperkalemia in the two arms. We will explore differences in the rates of ESKD or cardiovascular events and determine if there is any effect modification of the intervention by level of proteinuria or by diabetes. For patients lost to follow-up, we plan to use chained multiple imputation to perform analyses.

Sample size rationale

Randomizing 96 participants to strict vs usual BP control will provide 80% power (with 2-sided α of 0.05) to detect a 6-mmHg difference in SBP (with SD difference of 10 mmHg) between the two arms at month 8. Anticipating approximately 25% dropout, we plan to enroll 120 participants. An effect size of similar magnitude has been reported previously in telemonitoring feedback from pharmacists in adult home BP monitoring trials (37).

List of Abbreviations

BP- blood pressure

CKD- chronic kidney disease

CV- cardiovascular

SBP- systolic blood pressure

ESKD- end-stage kidney disease

SPRINT- Systolic Blood Pressure Intervention Trial

eGFR- estimated glomerular filtration rate

MDRD- Modification of Diet in Renal Disease

RAAS- renin-angiotensin-aldosterone system

AKI- acute kidney injury

BMP- basic metabolic panel

UPCR- urine protein creatinine ratio

ABPM- ambulatory blood pressure monitoring

DBP- diastolic blood pressure

MAP- mean arterial pressure

ARB- angiotensin receptor blockers

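### No masking of safety-event adjudication is described, and the adjudicators come from the group that titrates to the assigned target, so syncope and AKI could be classified differently by arm

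*Protocol*

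**What the plan says.** Study design (Protocol): "This pilot study is a non-blinded randomized controlled trial investigating the safety and feasibility of strict blood pressure control". Safety is thus a stated aim, and Outcomes measures makes it a secondary outcome. That outcome is a composite of hyperkalemia (potassium of 6.0 meq/L or more), falls reported by the participant, syncope, and AKI leading to an emergency visit or admission.

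On how events are confirmed, Outcomes measures says: "Discharge summaries from emergency room visits and hospitalizations in patient health records will be reviewed", with "events adjudicated by two study investigators".

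On who titrates, Home blood pressure readings says: "Antihypertensive medications will be titrated by study investigators based on the average of the most recent 18 home BP measurements received". Laboratory Tests adds: "Labs are closely monitored by study investigators and medications titrated".

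On who else knows the arm, Blood Pressure Targets says: "all nephrology clinic providers are alerted of patient enrollment in the study and the assigned BP target following randomization".

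The only masking of investigators that is mentioned is under Randomization: "Investigators will be blinded to the ordering of the randomization blocks and their respective sizes".

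Statistical analysis in the protocol and its counterpart in the SAP tally safety outcomes descriptively. They also test a different composite between arms: hospitalizations, emergency visits and hyperkalemia. The SAP does not mention adjudication.

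**The concern.** A study investigator cannot titrate to a target without knowing it, and the adjudicators are drawn from the group that titrates. Someone who knows the arm and may have set the regimen could then decide whether an admission counts as AKI, or whether a collapse counts as syncope.

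AKI is the most exposed component. The titration section tolerates a creatinine rise of up to 30% after a medication change. That is a rule for managing treatment; neither document gives a criterion for AKI as an event. An investigator who accepted a rise as an expected effect of treatment may later be asked whether the same participant's admission was for AKI. Syncope has no event definition either.

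Open-label treatment is unavoidable in a trial of blood pressure targets, but arm-aware adjudication from written records is not. What is at stake is the safety composite, one of the results that a pilot hands on to a larger trial.

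**Working it through.** **1. Could an adjudicator know the arm?** The documents support four steps.
- The trial is non-blinded (Study design).
- Study investigators titrate to the assigned target (Home blood pressure readings).
- Two people from the same named group adjudicate (Outcomes measures).
- Clinic providers are told the target (Blood Pressure Targets), so the health records may carry it. No redaction is described.

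The masking under Randomization covers block order and size. That protects allocation concealment and has no bearing on outcome assessment. Following the plan as written therefore allows arm-aware classification.

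**2. Which outcomes need judgement?**

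| Outcome | Basis | Exposed? |
|---|---|---|
| Hyperkalemia | Laboratory threshold | No |
| Falls | Participant report | Open to reporting bias, which masked review would not remove |
| Syncope | No stated criterion | Yes |
| AKI with emergency visit or admission | No stated event criterion | Yes |
| Tested composite (hospitalizations, emergency visits, hyperkalemia) | Record of contact, laboratory value | Largely not |
| Primary outcome (SBP separation at month 8) | Measured pressure | No |

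Cardiovascular events are outside the safety composite. They are only explored, and the text does not say whether adjudication covers them.

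**3. How large could the effect be?** The plan gives no figure to reproduce: no event rate, share of judgement-based events or confirmation rate. All inputs here are assumptions.
- True event proportion p = 20% in both arms.
- Judgement-based share of events j = 50%.
- Fraction of judgement-based events not confirmed in one arm m = 10% to 20%; none lost in the other arm.

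Observed proportion in the affected arm = p × (1 − j × m).
- m = 10%: 20% × (1 − 0.5 × 0.10) = 19%.
- m = 20%: 20% × (1 − 0.5 × 0.20) = 18%.

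If the loss is in the intervention arm, the risk ratio is 19/20 = 0.95 to 18/20 = 0.90. If it is in usual care, the risk ratio is 20/19 = 1.05 to 20/18 = 1.11. The true value is 1.00 throughout. The false risk difference is 1 to 2 percentage points.

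**4. Against sampling error.** Enrolling 120, with the first 75 at 2:1 and the other 45 at 1:1, gives about 50 + 22.5 = 72.5 and 25 + 22.5 = 47.5, taken as 72 and 48. At 20% in each arm, the 95% half-width of the risk difference is 1.96 × √(0.2 × 0.8/72 + 0.2 × 0.8/48) = 1.96 × 0.0745 = 14.6 points. The illustrated bias is small beside this.

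**The case against.** The strongest reply is that silence is not evidence of fault. These are a short public protocol and a one-page SAP. They do not say that records reach the adjudicators unmasked, and they do not say that the adjudicators titrated the participants whose events they judge. A reader might infer both; the text supports only that neither masking nor separation is described. That much of the reply stands.

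A reader might also infer that the whole safety conclusion is biased in favour of intensive control. If every event were open to judgement, the same losses would give 20% × 0.90 = 18% and 20% × 0.80 = 16%, a risk ratio of 0.80-0.90. The documents do not support this. Hyperkalemia has a threshold, falls are self-reported, the one safety comparison for which a test is planned is largely objective, and nothing indicates which arm would lose events.

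Two reviewers and source documents are real safeguards against random error. They do not protect against an expectation that both reviewers share, and no rule for disagreement is given. Wide sampling error limits how much the pilot can conclude on safety in any case, but it does not remove a bias that is cheap to reduce.

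Two practical objections also stand. The number of investigators is not stated, so there may be too few who did not titrate a given participant. The coordinator who would redact holds the allocation sequence. The second is tolerable if redaction follows a fixed list, since the coordinator would not classify events.

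**Conclusion.** The point holds in a limited form. The plan as written permits arm-aware adjudication of the judgement-based components of a secondary safety composite, chiefly syncope and AKI with emergency or hospital care. The possible distortion has no known direction. Under the assumed values it is a false risk ratio of 0.90-0.95 or 1.05-1.11, and it scales with the judgement-based share and the differential loss, neither of which the documents give. The primary outcome is untouched. This should be corrected because safety is a stated aim and the remedy costs little; it does not undermine the trial.

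**What to change.** Amend Outcomes measures, and repeat the text in the SAP, to say that:

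1. The coordinator removes arm, blood pressure target and study titration notes from discharge summaries before review, working from a fixed list of items.
2. Each event goes to two existing investigators who did not titrate that participant, where available. Where they are not, redaction and fixed criteria still apply, and the exception is recorded.
3. Event criteria for AKI and syncope are written down in advance and applied identically in both arms, with a rule for resolving disagreement.

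The SAP describes enrolment planning in the past tense and the protocol notes its own publication in 2021, so some events may already have been adjudicated; the documents do not say. For those, re-review redacted copies on the same terms. If that is not possible and adjudication was unmasked, disclose it and report the objective components (hyperkalemia, hospitalizations, emergency visits) separately as a sensitivity analysis.

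The cost is some coordinator time, a short amendment and, for past events, the time of a second review. No new staff are needed. Masking will be partial, because medication lists or clinic notes may hint at the arm. It will not address reporting bias in falls.

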The timeline of study visits during the one-year of follow-up is outlined in Figure 1. Participants are instructed to take weekly home BP readings for the first 4 months of the study, or until target SBP levels are achieved for two consecutive weeks. Once participants reach target SBP levels, home BP readings can be taken on a monthly basis over a one-week period each month. If participants maintain their target SBP levels after 8 months, home BP readings can be taken every two months thereafter. Participants will maintain their respective SBP target levels for the remainder of the study after month 8. If mean weekly SBP readings are > 4 mmHg outside the target range, antihypertensive therapy titration is resumed weekly until target SBP levels are achieved again for two consecutive weeks.

Participants are seen in person at Months 2, 4, 8, and 12, and every 6 months thereafter, but visits will be timed as close to their clinical visits as possible to avoid additional burden on participants in a pragmatic approach. In-person follow-up visits consist of a brief physical exam, office BP readings which will be obtained and used to calibrate the QardioArm® device to ensure accuracy of its readings, and laboratory testing. Patients will be contacted throughout the study via phone or secure text messages depending on patient preference. Adherence to antihypertensive therapy treatment will be assessed by administering a questionnaire during every in-person visit and follow-up phone call to ask participants if they are taking antihypertensive medications as prescribed and if they missed any doses since last follow-up. Adverse events (including emergency room visits or hospitalizations) and onset of ESKD, defined as initiation of chronic dialysis or receipt of kidney transplant, are also ascertained during follow-up. Participants will be followed indefinitely unless they choose to disenroll from the study or are lost to follow-up.

Outcomes measures

The primary outcome will be feasibility of achieving at least a 6 mmHg separation between intensive BP control and usual BP control arms at month 8. A secondary outcome will be the difference in BP between the two treatment strategies at study closeout. Adherence to home BP monitoring will be measured by the number of weeks participants successfully complete the minimum number of home readings.

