PERFORMANCE Trial

NCT02975505

Document date: 2/13/2025

Statistical Analysis

Safety outcomes, or rates of adverse events, will be tallied using simple proportions and descriptive statistics. Intention-to-treat analysis will be performed. Stratified analyses by diabetes status will be performed given the lack of robust trial data to support intensive BP lowering in patients with diabetes. We will also test for differences in the composite rates of hospitalizations, emergency room visits, and hyperkalemia in the two arms. We will explore differences in the rates of ESKD or cardiovascular events and determine if there is any effect modification of the intervention by level of proteinuria or by diabetes. For patients lost to followup, we plan to use chained multiple imputation to perform analyses.

Sample Size Rationale

We estimate that randomly assigning 90 participants to intensive versus less intensive SBP control would provide 80% power (with 2-sided α of 0.05) to detect a 6-mmHg difference in SBP (with SD of the change in SBP within each arm to be 10 mmHg) between the two arms at month 12. Anticipating approximately a 20% dropout rate given the pill burden and 10% loss to follow-up rate given the traditional known challenges in recruiting and retaining patients with advanced CKD to an interventional trial, we planned to enroll up to 120 participants

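### Protocol and SAP, dated the same day, power different time points (month 8 and month 12), and the protocol's 120 leaves 90 after 25% dropout, not the 96 it requires

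*Protocol*

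**What the plan says.** The protocol (title block: "Document date: February 13, 2025") and the SAP (title block: "Document date: 2/13/2025") each contain one power paragraph.

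| | Protocol, Sample size rationale | SAP, Sample Size Rationale |
|---|---|---|
| Required number | "Randomizing 96 participants to strict vs usual BP control will provide 80% power" | "randomly assigning 90 participants to intensive versus less intensive SBP control would provide 80% power" |
| SD and time point | "with SD difference of 10 mmHg) between the two arms at month 8" | "with SD of the change in SBP within each arm to be 10 mmHg) between the two arms at month 12" |
| Attrition | about 25% dropout | about 20% dropout, and 10% loss to follow-up |
| Enrolment | "Anticipating approximately 25% dropout, we plan to enroll 120 participants" | up to 120 |

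The 6 mmHg difference, the value of 10 mmHg for the SD, the two-sided 5% level and the 80% power are the same in both.

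The protocol's Outcomes measures section defines the primary outcome as "feasibility of achieving at least a 6 mmHg separation between intensive BP control and usual BP control arms at month 8". Its secondary BP comparison is at study closeout. The Randomization section allocates 2:1 for the first 75 participants and 1:1 after that. Neither sample-size paragraph states an allocation ratio or a test.

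**The concern.** There are two separate problems.

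The first is the time point. Month 12 is a study visit, but the protocol sets no outcome there. The SAP names no primary outcome, and its power sentence gives the only time point it has for the BP comparison. Someone working from the SAP alone would take month 12 as the main comparison; someone working from the protocol would take month 8. With identical dates, neither document can be said to supersede the other. The choice of primary comparison should not be left open in this way.

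The second is the arithmetic. The power calculation is the stated basis for enrolling 120, yet the protocol's enrolment figure does not deliver the number it says it needs. The SAP's may or may not, because it does not say whether its 20% and 10% overlap, or whether both remove the BP outcome.

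**Working it through.** **Inputs.** Difference 6 mmHg, SD 10 mmHg, two-sided α 0.05 and power 80% (both sample-size paragraphs). Allocation from the protocol's Randomization section: 50:25 for the first 75, then 22.5:22.5 for the next 45, so 72.5:47.5 of 120 on average. The arm fractions are p = 0.604 and q = 0.396, with pq = 0.2391. I take 10 mmHg as the within-arm SD, as the SAP does.

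**1. The required numbers.** By normal approximation, N = (1.960 + 0.842)² × (10/6)² / (pq) = 7.849 × 2.778 / (pq) = 21.80 / (pq).

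- 1:1 (pq = 0.25): 87.2, or 88 as 44 per arm. By t-test, 89.2. With 90, t-test power is 80.4%. This reproduces the SAP's 90.
- 72.5:47.5: 21.80/0.2391 = 91.2. By pooled t-test, 93.1. In whole numbers, 92 and 94 evaluable out of 120 randomized.
- Exactly 96 randomized in the planned sequence (60.5:35.5): t-test power 80.2%. With 95 it is 79.7%. This is consistent with the protocol's 96.

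So neither base number is wrong in itself. The protocol's fits the planned allocation; the SAP's fits 1:1 throughout, which is not the planned allocation.

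**2. The protocol's inflation.** The enrolment needed to keep n after a loss d is n/(1 − d).

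- 96/(1 − 0.25) = 128.
- 96 × 1.25 = 120, which reproduces the stated figure by the wrong formula.
- 120 × (1 − 0.25) = 90, which is 6 short of 96.
- 120 yields 96 only at 20% loss: 120 × 0.80 = 96.

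**3. What the SAP's two rates leave of 120.**

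- Distinct losses, both removing the outcome: 120 × 0.70 = 84 if added, or 120 × 0.80 × 0.90 = 86.4 if multiplied.
- The 10% lies within the 20%: 120 × 0.80 = 96.
- Only the 10% loss to follow-up removes the outcome: 120 × 0.90 = 108.

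The last reading is possible but not established. The protocol keeps following participants until they disenroll or are lost, and the analysis is by intention to treat, but dropout may also mean leaving the study.

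**4. Power at 72.5:47.5.** By normal approximation, power = Φ(0.6 × √(N × pq) − 1.960). For N = 90: 0.6 × √21.52 = 2.784, and Φ(0.824) = 79.5%. The t-test column uses the noncentral t distribution.

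| Evaluable | Loss from 120 | t-test | Normal approx. | Difference detectable with 80% power (t-test) |
|---|---|---|---|---|
| 84 | 30% | 75.7% | 76.7% | 6.33 mmHg |
| 86.4 | 28% | 76.9% | 77.9% | 6.24 mmHg |
| 90 | 25% | 78.6% | 79.5% | 6.11 mmHg |
| 96 | 20% | 81.2% | 82.0% | 5.91 mmHg |
| 108 | 10% | 85.6% | 86.2% | 5.56 mmHg |

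**5. Break-even loss with 120 enrolled.** 1 − 93.1/120 = 22.4% by t-test; 1 − 91.2/120 = 24.0% by normal approximation.

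**6. Sensitivity with 90 evaluable.** An SD of 9.83 restores 80%; an SD of 10.5 gives 74.6%. Attrition of 30% in the intervention arm and 17.4% in usual care gives 79.7%; 20% and 32.6% gives 76.9%.

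**The case against.** The strongest reply is that the inflation slip hardly matters. The 90 participants left after 25% dropout are exactly the number the SAP says gives 80% power, and a 1:1 t-test agrees (80.4%). The shortfall appears only once the planned unequal allocation is applied, and then it is 1.4 points by t-test or 0.5 by normal approximation. The dropout rate is only approximate, and the normal-approximation break-even is 24.0%. Baseline adjustment would also close the gap: a baseline correlation of 0.2, which is an assumption because neither document specifies the model, gives 80.2%. In a pilot with a feasibility outcome, this is not a material loss.

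That stands as to size. It does not make 120 × 0.75 equal 96, and the unequal allocation is the protocol's own.

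Two further points stand in part. The SAP range of 76% to 86% spans 80%, so it shows an ambiguity and not a demonstrated shortfall. And the 94 or 92 applies to evaluable participants out of 120 randomized; it does not displace the 96 if exactly that many are randomized in sequence, where 94 would give 79.2%.

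It can also be said that the protocol agrees with itself on month 8 and that the outlier is one phrase in the SAP. That is true, but the SAP is the document that governs the analysis, and nothing in either document says which time point prevails.

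**Conclusion.** The concern holds. Two documents of the same date power different time points, with different required numbers, attrition and SD wording. Only the protocol's month 8 matches the stated primary outcome. This conflict matters most, and it does not depend on any calculation.

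The protocol's enrolment figure is also wrong on its own inputs: 90 remain, not 96. The effect is small, with power about 79% in place of 80%, or 80% power for 6.1 mmHg. Whether the SAP's 120 is enough cannot be settled from its text; it falls short only if its two losses are distinct and both remove the outcome.

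These figures assume a within-arm SD of 10 mmHg, an average split of 72.5:47.5, all 120 randomized, equal attrition by arm, no baseline adjustment and nothing recovered by the planned multiple imputation. It should be fixed, but it does not call for a larger trial.

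**What to change.** Keep 120 and put the same power statement in both documents. It should give:

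- the time point. Month 8 matches the primary outcome. If the sponsor says month 12 is current, the protocol's Outcomes measures section must be reconciled too;
- 10 mmHg defined as the within-arm SD, saying whether of SBP or of its change;
- the planned allocation, about 72.5:47.5 of 120;
- one total rate of missing outcome, chosen because it is plausible and not to fit the number, saying whether the SAP's 20% and 10% overlap and whether participants who stop treatment still supply BP;
- the evaluable number, as 120 × (1 − loss);
- the resulting power under a named test. By pooled t-test this is about 86% at 10% loss, 81% at 20%, 79% at 25%, and 76–77% at 28–30%.

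If a required number is quoted, label it as evaluable out of 120 randomized: about 94 by pooled t-test or 92 by normal approximation. The figure of 90 holds only for a 1:1 t-test. The SAP describes enrolment in the past tense; if recruitment is complete, the restated power should be labelled as retrospective.

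If month 8 stands, the cost is rewording, with no added patients and no change to conduct. The stated power may move to between about 76% and 86%, and to about 79% on the protocol's own 25%. Adopting month 12 would be a larger step, because it changes the time point of the primary outcome.
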